3.4 Randomization and Blinding

The randomization scheme for the study will be provided by the Research facility.

Each subject will receive two treatments. Assignment of products to the left or right side for each body area will be per a computer-generated randomization schedule.

Specific sites of sampling for baseline and post application sampling time points will be randomized.

Randomization will continue until required number of subjects with required treatment day baseline counts is enrolled.

The PI is responsible for ensuring that the randomization is followed. The randomization schedule for the groin sites will be provided in a separate document. The study products will be labeled with the appropriate codes provided in Table 1.

Each subject will be identified by their initials and a subject number for which they qualify. Inclusion subject numbers will be assigned at Treatment day.

- Washout subjects will be assigned numbers starting with 001 and the letter "P": P001
- Treatment subjects will be assigned numbers with 001 and the letter "I": I001

The study products will not be blinded from the PI or other study staff performing the study material application or bacterial sample collections. The staff member(s) performing bacterial enumeration and the statistician will be blinded from the identification of treatment assignment. The study staff performing the bacterial enumeration will not be involved in the study products application or the collection of samples. The Raw Data Sheet sections of the CRF will be maintained separately (from the pages within the CRF which include study treatment identifications) during the conduct phase of the study. The study staff performing the bacterial enumeration will record counts directly onto the Raw Data Sheet pages of the CRF without accessing the subject study documentation folder containing the other CRF pages. The Raw Data Sheets will be compiled with the entire CRF after all data recording have been completed.

The generated randomization scheme will contain the following treatment codes: P1, P2, P3 and P4 to ensure the blinding for the study statistician. The assignment between the treatment codes (P1, P2, P3 and P4) from the randomization scheme and the label treatment codes (A, B, C and D) will be made by the Sponsor in a separate document.

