In this study four products will be tested and each subject will receive two products in the same time, one on the left side and the other on the right side. More than 100 randomization schemes will be generated to compensate for the baseline requirement failure and to provide enogh evaluable sites. The block randomization method will be used to ensure equal sample size groups over time. Products will be randomized in blocks of 12 and sampling time points will be randomized in blocks of 6. Randomization scheme will be generated using an electronic online randomizer provided by Urbaniak et al. (2013).

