5.1.2.1.1 Preparation of Groin Test Area

The test site within the groin region (groin test area) is defined as the inner aspect of the uppermost thigh, one inch parallel distance to the inguinal crease and where skin to skin contact is expected. Where subjects present with deep inguinal folds at the crease, the sampling distance from the crease may be increased to avoid skin folds in the sampling area. The corners of each groin test area will be marked directly on the skin using a non-toxic skin marker. Three sampling sites will be numbered within each groin test area, on each side of the groin region. The positioning and numbering of the groin sampling sites are standard for all subjects. Sampling sites on the contra-lateral side of the groin will be numbered in a mirror-image orientation. The three sampling sites within each test area represent one baseline (pre-prep) site and two post-prep sample sites (30 seconds and 10 minutes).

Test sites for the investigational product and active control applicator on the groin will be $1.5'' \times 5''$ (3.81 cm x 12.7 cm) in area, occur at the uppermost inner aspects of both thighs, and appear to be similar in condition.

After groin test areas are marked and sample sites numbered, baseline samples will be collected from the appropriate site per the randomization schedule in each test area using the scrub cup technique (section 5.2.1).

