5.1.2.2 Study Products Application

The randomization schedule will designate the treatment to each side of the groin.

Following baseline sample collection, randomly assigned contra-lateral test areas will be treated with the applicable study products. The post-application sampling times will be randomized among the sampling sites within a test area.

The study products will be applied and the sampling configurations will be performed per the randomization scheme and the Treatment Application Instructions (Appendix 17.6). The duration of each application procedure will be recorded on the appropriate CRF. The study products, body area, application and dry times and treatment area are summarized in Table 2.

Products	Body Area	Application Time	Drying Time	Treatment Area
26 ml Project X (A)	Groin	120 seconds	min. 180 seconds	1.5" x 5.0" (3.81 cm x 12.7 cm)
10.5 ml Project X (B)	Groin	120 seconds	min. 180 seconds	1.5" x 5.0" (3.81 cm x 12.7 cm)
5.1 ml Project X (C)	Groin	120 seconds	min. 180 seconds	1.5" x 5.0" (3.81 cm x 12.7 cm)
Prevantics® Maxi Swabstick 5.1 ml (D)	Groin	120 seconds	90 seconds	1.5" x 5.0" (3.81 cm x 12.7 cm)

Table 2: Study products, body area, application and dry times and treatment area

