9.3 Efficacy Analyses

An alpha level of 5% will be used for all analyses.

The following descriptive statistics for log_{10} CFU/cm² and for log_{10} CFU/cm² reductions from Baseline will be computed for each treatment, grouped by body area and each post application sampling time point (30 seconds, 10 minutes and/or Baseline, by case): mean, median, standard deviation, minimum, maximum, and count.

The statistician will be blinded to the treatment during the analysis phase.

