9.3.1 Efficacy Analysis

A linear regression model for each post treatment sampling time point of immediate efficacy (30 seconds and 10 minutes post-application) will be used. In the model, the dependent variable used will be the post treatment bacterial count (\log_{10} CFU/cm²) and predictors will be the treatment as a fixed effect and the Baseline as a covariate. The ATE corrected for Baseline will be estimated from the model and compared to non-inferiority criteria.

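### Side, sampling position and enrolment block are built into the randomisation but left out of the efficacy model, which costs some precision

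*Combined protocol and SAP*

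**What the plan says.** **Side.** Each subject receives two of the four products, one per groin side. Section 3.4: "Assignment of products to the left or right side for each body area will be per a computer-generated randomization schedule".

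**Position.** Each test area holds three numbered sites, one for baseline and one for each post-application time. Section 5.1.2.2: "The post-application sampling times will be randomized among the sampling sites within a test area". Section 5.1.2.1.1 fixes the layout: "Sampling sites on the contra-lateral side of the groin will be numbered in a mirror-image orientation".

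**Blocks.** Section 3.4 states "Products will be randomized in blocks of 12 and sampling time points will be randomized in blocks of 6". Its declared purpose is "The block randomization method will be used to ensure equal sample size groups over time".

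**Model.** Section 9.3.1 plans "A linear regression model for each post treatment sampling time point of immediate efficacy", in which "predictors will be the treatment as a fixed effect and the Baseline as a covariate". The synopsis says the same. Neither place has a term for side, position or block, and no sensitivity analysis adds one. Section 9.3 adds: "An alpha level of 5% will be used for all analyses". The upper bound of the two-sided 95% interval for A-D, B-D or C-D is compared with 0.5 log10.

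**The concern.** Factors that structure a randomisation are normally carried into the analysis. Here they are known for every site at no extra effort. If counts differ between left and right, along the test area or over the enrolment period, the planned model treats those differences as noise. The interval is then wider than it need be, and non-inferiority is harder to show.

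Position raises a second issue. Section 3.4 gives separate block sizes for products and for sampling time points. If the two were generated separately, a product could by chance be sampled more often at one end of the test area than its comparator. The planned model would not remove that difference from the realised contrast.

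The question matters more because section 9.2 says that no sample size calculation was done, so precision against the 0.5 margin is not assured.

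**Working it through.** **1. The plan's own figure.** 100 subjects x 2 sites / 4 products = 50 sites per product. This matches the minimum in 9.2, provided no site is lost. No SD or power is stated, so none can be reproduced.

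**2. What the block sizes suggest.** Four products give 4 x 3 = 12 ordered left/right pairs. Three samples over three sites give 3! = 6 orders. Both match section 3.4 exactly, but the text does not say what fills a block. The example scheme in Appendix 17.3 has one set of Site 1 to 3 columns per randomization number, which suggests one position order per subject. Steps 3 to 5 assume these readings and separately generated lists.

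**3. Chance position imbalance, A versus D.** Score each subject +1 if given A only, -1 if given D only, and 0 otherwise (neither, or both, where a shared order cancels). A block of 12 has four +1, four -1 and four 0, so the sum of squares is 8. A given position takes the post sample in 4 of 12 subjects.
- Count difference at one position, variance per block: 8 x (1/3)(2/3) x 12/11 = 1.94. Over nine blocks (108 subjects) the SD is sqrt(9 x 1.94) = 4.2 sites out of 54.
- Linear end-to-end gradient g, with site scores -g/2, 0 and +g/2: variance per block is 8 x (g²/6) x 12/11 = 1.455 g². With 108 subjects the SD of the shift in A-D is sqrt(9 x 1.455) g / 54 = 0.067 g. With 100 subjects it is sqrt(8.33 x 1.455) g / 50 = 0.070 g.
- For assumed g of 0.25, 0.5 and 1.0 log10 and 100 subjects, the SD is 0.017, 0.035 and 0.070 log10. Simulated 95th percentiles are about 0.035, 0.07 and 0.13 to 0.14, or 7%, 14% and 27 to 28% of the margin.
- If left and right orders were drawn independently, the SD at g = 0.5 would be 0.043.

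**4. Precision.** Simulation used 3,000 trials per case, 100 subjects, true difference 0 and no within-subject correlation. The assumed effects are position spread / side / enrolment drift, in log10. The adjusted model adds side, position and block.

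| Assumed effects | Residual SD | SE of A-D, planned → adjusted | Power, planned → adjusted |
|---|---|---|---|
| small 0.25/0.1/0.25 | 0.8 | 0.163 → 0.161 | 86.3% → 86.6% |
| medium 0.5/0.25/0.5 | 0.8 | 0.171 → 0.162 | 83.1% → 86.1% |
| medium 0.5/0.25/0.5 | 1.2 | 0.247 → 0.242 | 52.0% → 53.2% |
| large 1.0/0.5/1.0 | 0.8 | 0.197 → 0.162 | 73.9% → 86.8% |
| none | 1.2 | 0.2400 → 0.2417 | 53.8% → 53.2% |

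The last row is the cost when nothing is there to remove: 0.2417 / 0.2400 = 1.007, an interval 0.7% wider.

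A second set used 108 subjects, residual SD 0.9 to 1.0, and gradient / side / block SD of 0.3/0.1/0.1, 0.5/0.2/0.2 and 0.8/0.3/0.3. Power went from 72% to 73%, 75% to 77% and 73% to 81%. The half-width went from 0.385 to 0.383, 0.378 to 0.363 and 0.384 to 0.345.

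**5. Validity of the planned model.** At a true difference of 0.5, it declared non-inferiority in 1.1% to 2.8% of simulated trials (nominal 2.5%, simulation error about 0.3 points). Mean bias was negligible. Under large effects the planned SE was conservative: at SD 1.2 the mean SE was 0.267, against an actual SD of the estimate of 0.252.

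**The case against.** **No validity problem.** A reader might infer that a position gradient biases A-D, B-D and C-D, or that the trial could falsely pass. The documents do not support this. Position and side are randomised, so imbalance averages out over schedules and is ordinary randomisation error. Step 5 shows no meaningful inflation of the error rate. This part of the objection stands in full.

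**The design reading is inferred.** A block of 12 could instead be 12 product allocations, that is six subjects with each unordered pair once, which would not guarantee side balance. Appendix 17.3 shows products and sites on one row, and the actual schedule is in a separate document. It therefore cannot be established that product-by-position balance is left to chance. This stands as a limit on step 3. It does not affect the omission of the factors from 9.3.1.

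**Balance over side and block.** A reader might also take blocking to mean that the contrasts are already free of side and enrolment effects. Section 9.1 accepts or drops left and right sites separately on baseline count, and 100 is not a multiple of 12, so that balance need not survive into the analysed sets. This favours adjustment.

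**Small and assumed.** No gradient, side effect or drift is given in the documents. Baseline is taken in the same test area on the same day and may absorb part of the side and enrolment variation. Sampling time is already handled by separate models, so only enrolment time is at issue. All of this stands and keeps the point modest.

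**The missing subject term matters more.** The model also ignores that each subject gives two sites. At correlation 0.4 and SD 0.8 the planned SE is 0.156 against a true 0.145. That is a separate gap, but it constrains how this one should be fixed.

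**Conclusion.** The point holds as a precision improvement. The model in 9.3.1 leaves out side, sampling position and enrolment block, all of which the randomisation uses or records. Their variation stays in the residual, and the realised position imbalance stays unadjusted. The planned estimate remains unbiased, with an error rate at or near nominal, so nothing here invalidates a non-inferiority conclusion.

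The gain is roughly 0 to 1 power points for small effects, 1 to 3 for medium and 8 to 13 for large, against about 0.5 points lost if none matters. These figures rest on assumed effects and residual SDs of 0.8 to 1.2 log10, a true difference of 0, and the inferred block structure with one position order per subject. The change is worth making because it is cheap and the possible loss is small. It is not essential.

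**What to change.** In 9.3.1 and the synopsis, prespecify these added predictors in the model at each time point: side (left/right), position of the post-treatment sample (1/2/3) and position of the baseline sample (1/2/3). Add randomization block as a further term, for example random.

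If a subject term is also added for the two sites per subject, make it random. Block is constant within subject, and so is position if one order serves both sides. A fixed subject term would then alias both and leave only side estimable, 1 of the 13 added degrees of freedom.

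If the schedule has not yet been generated, produce the position orders jointly with the product pairs so that each product meets each position about equally often. State in section 3.4 what makes up a block of 12 and a block of 6, and whether one order serves both sides.

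**Cost:** wording only, with no extra subjects or data. With nine fixed blocks the terms use 1 + 2 + 2 + 8 = 13 of roughly 200 degrees of freedom, and the interval is under 1% wider if none of the factors has an effect. The terms should be fixed before counts are seen, since covariates chosen afterwards would be open to challenge.

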3.5 Study Products

The products identified in Table 1 will be used in the study. Specific product identification codes and lot numbers will be included with the clinical supplies when they are shipped to the Research facility.

Treatment Denomination Volume Description 26 ml Project X 26 ml 3.15 % w/v CHG / 70% v/v IPA В 10.5 ml Project X 10.5 ml 3.15 % w/v CHG / 70% v/v IPA С 5.1 ml Project X 5.1 ml 3.15 % w/v CHG / 70% v/v IPA 5.1 ml D Prevantics® Maxi Swabstick 3.15 % w/v CHG / 70% v/v IPA

Table 1: Study Products

PDI is responsible for analytically testing (content and purity) the study products to ensure they comply with their specifications and both released as per approved specifications of the marketed control product.

3.5.1 Study Products Labeling

PDI will label, package, and ship the study products to the research facility. ER personnel will document receipt and storage of the study materials.

3.5.2 Product Incidents

A Product Incident is defined as any problem or issue involving the investigational product(s). PDI and Study Monitor should be contacted immediately when site becomes aware of or suspects:

- Product damaged upon visual inspection
- Product damaged upon removal/preparation
- Product packaging damaged/broken
- Product failure or malfunction
- Product handling issue
- Product lacking liquid antiseptic

Product considered as Product incident should be quarantined and returned with appropriate documentation to the PDI unless instructed otherwise by PDI

3.6 Study Supplies

3.6.1 Study Supplies Provided by Sponsor

- Study Products

3.6.2 Study Supplies Provided by Research facility

- Product kits (toiletry items to be used by subjects during study)
- Stripping Suspending Fluid with product neutralizers (SSF++) containing 1.01% Na₂HPO₄, 0.04% KH₂PO₄, 0.1% Triton X-100, 1.167% Lecithin, 10% Polysorbate 80, 0.5% Na₂S₂O₃ \bullet 5H₂O, and 1% TamolTM (pH 7.9 \pm 0.4)
- Butterfield's sterile phosphate-buffered water (PBW), 312 μ M KH₂PO₄ (pH 7.2 \pm 0.4)
- Trypticase soy agar containing 0.5% Polysorbate 80 and 0.07% lecithin (TSA+N)
- Disposable Pasteur Pipettes, sterile
- Tubes with sealable caps, polypropylene or glass, sterile
- Petri dishes, 90 mm, sterile
- Gloves, sterile
- Gauze, sterile
- Non-toxic marking pen: Chemo Skin Marker- Regular™
- Rubber policemen, sterile
- Scrub cups (2.20 cm I.D., 3.80 cm²), sterile
- Timers
- Pipette Aid or similar apparatus
- Vortex mixer
- Surgical Clipper & clipper blades: 3M Surgical Clipper
- Culture Media Preparator
- Peristaltic Pump
- Incubator (30 \pm 2°C)
- Disposable underwear for subjects
- urine pregnancy test (UPT)
- Biological safety cabinet

- Manual colony counter
- pH-meter

3.7 Study Duration

The expected duration of this study for each subject is up to 3 weeks. Subjects will undergo at least a 14-day washout period before Treatment Day. The treatment day will be scheduled no sooner than 14 days from the washout visit. Each subject who chooses to participate in this study will be required to stay in the test facility for one scheduled Treatment Day.

3.8 Study Termination/Subject Discontinuation or Withdrawal

3.8.1 Study Termination

PDI or the PI has the right to discontinue the study at any time for medical and/or administrative reasons. As much as possible, this should occur after mutual consultation.

3.8.2 Subject Discontinuation and Withdrawal

The PI may discontinue individual subjects from the study at any time. Subjects may voluntarily withdraw from the study at any time without reason or consequence. A reason will be reported, if provided. The PI will provide a written report on the appropriate CRF including the date and reason for discontinuance.

Additional subjects will be recruited, as necessary, to meet the required number of evaluable treatment sites per treatment, per collection time.

3.9 Study Product Accountability

PDI requires PI to maintain accountability and adequate inventory security of the study material at all times. The PI or designated sub-investigator trained by the PI will:

- complete the Confirmation of Receipt form upon receipt of the shipment and maintain and account for inventory on the Study Material Disposition form.
- keep study materials in a secure storage area, accessible only to authorized individuals.
- dispense study material only to subjects properly enrolled into the study.
- destroy all used study materials during the technical execution of the study
- return all study materials involved into Product incident and/or AE/SAE to PDI upon Sponsor agreement.
- return or destroy all unused study materials to PDI at the end of technical execution of the study upon Sponsor agreement.

Before starting the study, investigational products and positive control product will be supplied and shipped to the site by PDI and stored at controlled room temperature avoiding freezing and heat above 40°C. A sample from each product will be kept in the sample storage area of the Research facility for at least 3 years after the end of the study, then destroyed, according to the corresponding procedure of the Research facility.

3.10 Source Data

Source data includes any original documents, data and records where any data are first recorded (e.g., ICFs, laboratory notes, etc) used for study traceability. If data are recorded for the first time directly onto the CRF, then the CRF is considered the source document for these data.

3.11 Protocol Modifications

3.11.1 Protocol Amendments

Protocol Amendments will not be implemented without prior agreement between the PI and PDI and prior submission and approval from the IRB/EC, except when necessary to eliminate an immediate hazard to the subject and to protect the safety and well-being of the subject.

Will constitute Protocol Amendments for administrative inputs and changes: correction of typing mistakes, changes in study personnel (other than the PI) or contact information. Protocol Amendments for administrative inputs and changes has to be agreed between the PI and PDI and will be submitted to the IRB/EC but implementation may proceed without prior IRB/EC approval, unless so required by the IRB/EC or site SOPs.

3.11.2 Protocol Deviations

A deviation is a departure from the protocol that will likely affect the safety, rights or welfare of subjects, the scope of the investigation, the integrity of the data or the scientific quality of the study. Protocol deviations are documented on a Protocol Deviation Form.

Deviations that potentially affect 1) subject safety, rights or welfare, 2) data integrity or 3) compromise the statistical analysis of the study require communication to PDI at the earliest convenience.

A Protocol Deviation Form must be completed by the PI or designated sub-investigator trained by the PI and checked and approved by PI and include a description of the circumstances surrounding and the reason for the deviation, any actions taken, and whether or not the subject was allowed to continue in the study.

If during monitoring visits a deviation is identified, the Study Monitor will report it to the PI and PDI.

4 Study Population

The trial will utilize ER's subject database and would not require the recruitment of subjects through study-specific advertisement.

Subjects must satisfy all Treatment Day Inclusion/Exclusion Criteria prior to Treatment Day procedures.

Treatment Day Baseline microbial count requirements are in the range of 5.00 to 7.50 log_{10} CFU/cm², inclusive, on the groin.

Additional subjects will be recruited and treated as necessary, to meet the required number of evaluable treatment sites per collection time.

All subjects will be given verbal and written information about the study procedures - Subject Instructions for Main Study (Appendix 17.5) will be provided to each subject for the Washout phase of the study.

